5.3 OPTIMIZATION ENDPOINTS

5.3.1 Endpoint 1: Intra-procedure Pain

Procedural pain will be assessed using the Wong Baker scale. Subjects will be asked to rate the level of pain and discomfort during the treatment.

5.3.2 Endpoint 2: Post-Procedure Catheterization

All subjects will be kept at the clinic for observation for 24 hours post-procedure. Post procedure catheterization will only be allowed if the Principal Investigator determines that

the subject has symptoms of retention (defined as failure to void within 8 hours post procedure) or requires catheterization for other safety reasons.

5.3.3 Endpoint 3: Lesion size, as measured by MRI at Week 1 post-procedure.

5.3.4 Endpoint 4: Change in IPSS score from baseline at various points post-procedure.

5.4 INCLUSION CRITERIA

- 1. Male subjects \geq 45 years of age who have symptomatic / obstructive symptoms secondary to BPH requiring invasive intervention.**
- 2. IPSS score of \geq 15.**
- 3. Qmax: Peak flow rate \leq 15 ml/sec.**
- 4. Post-void residual (PVR) $<$ 300 ml.**
- 5. Prostate transverse diameter $>$ 30 mm.**
- 6. Prostate volume between 20 to 120 gm.**
- 7. Voided volume \geq 125 ml.**
- 8. Subject able to complete the study protocol in the opinion of the Principal Investigator.**
- 9. Subject must be willing to undergo the procedure without anesthesia.**

5.5 EXCLUSION CRITERIA

- 1. History of any illness or surgery that in the opinion of the Principal Investigator may confound the results of the study.**
- 2. Presence of a penile implant.**
- 3. Any prior minimally invasive intervention (e.g. TUNA, Laser, Microwave) or surgical intervention for the symptoms of BPH.**
- 4. Currently enrolled in another clinical trial.**
- 5. Confirmed or suspected malignancy of prostate or bladder.**
- 6. Previous rectal surgery (other than hemorrhoidectomy) or history of rectal disease.**
- 7. Previous pelvic irradiation or radical pelvic surgery.**
- 8. Documented active urinary tract infection by culture or bacterial prostatitis within last year documented by culture (UTI is defined as $>100,000$ colonies per ml urine from midstream clean catch or catheterization specimen).**
- 9. Neurogenic bladder or sphincter abnormalities.**
- 10. Urethral strictures, bladder neck contracture or muscle spasms.**
- 11. Bleeding disorder (note that use of anti-platelet medication is not an exclusion criterion).**
- 12. Subjects who are interested in maintaining fertility.**
- 13. Use of concomitant (or recent) medications to include the following:**
 - a. Beta blockers, antihistamines, anticonvulsants, and antispasmodics within 1 week of treatment, unless there is documented evidence of stable dosing for last 6 months (e.g., no dose changes).**
 - b. Alpha blockers, antidepressants, anticholinergics, androgens, or gonadotropin-releasing hormonal analogs within 2 weeks of treatment.**
 - c. 5-alpha reductase inhibitor within the last 6 months**
- 14. Subject is unable or unwilling to go through a “washout” period for the above medications prior to treatment.**

- 15. Subject has chronic urinary retention.**
- 16. Significant urge incontinence.**
- 17. Poor detrusor muscle function.**
- 18. Neurological disorders which might affect bladder or sphincter function.**
- 19. Bladder stones.**
- 20. Renal impairment.**
- 21. In the opinion of the Principal Investigator, subject will not be able to adequately tolerate a rigid cystoscopy-type procedure.**
- 22. Unable or unwilling to sign the Informed Consent Form (ICF) and/or comply with all the required follow-up requirements.**
- 23. Any cognitive disorder that interferes with or precludes a subject from directly and accurately communicating with the Principal Investigator regarding the study.**
- 24. Peripheral arterial disease with intermittent claudication or Leriches Syndrome (i.e., claudication of the buttocks or perineum).**
- 25. Biopsy of the prostate within 30 days prior to the Rezūm procedure.**

6 STUDY PROCEDURES

6.1 SUBJECT ENROLLMENT

Only subjects who meet the inclusion/exclusion criteria will be eligible to participate in the study. It is recommended that only subjects that live within 90 minutes of driving distance from the study site be selected as participants in the study due to the study follow-up requirements.

Once it is determined that a subject meets the enrollment criteria (except for the use of the concomitant medication), the subject will be given an informed consent to read. Subjects that were on BPH medication will then go through a washout period. If the subject successfully goes through the washout period and still meets the selection criteria, the subject will be considered enrolled and assigned an enrollment ID.

The Principal Investigator (PI) or study coordinator will review the informed consent with the subject to be sure the subject completely understands the meaning of the consent. Upon completion, the subject will be given an opportunity to sign the informed consent. A subject will be considered officially enrolled only if treatment with the NxThera Rezūm System is attempted.

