6.2 SCREENING AND BASELINE EVALUATIONS

The following evaluations will be completed for all study candidates who have provided a written informed consent:

- Complete general medical and genitourinary history (including any previous treatment for LUTS; if pharmacologic, name of drug(s) as well as dosage) and duration of subject's BPH symptoms.**
- Blood analysis:**
 - Complete blood cell count (CBC)**
 - Blood urea nitrogen (BUN)**

- Serum creatinine
- Serum prostate-specific antigen (PSA) level
- Electrolytes
- **Uroflowmetry:**
 - Voided volume (must be ≥ 125 mL or test must be repeated)
 - Total time of voiding
 - Peak flow rate (Q_{max}; also known as PFR)
 - Average urinary flow rate
 - Post-void residual urine volume (PVR; may be measured by either ultrasound or catheterization but the same method must be used pre- and post-treatment)
- **Urinalysis**
 - Urine culture, if indicated
 - Subject questionnaires:
 - International Prostate Symptom Score (IPSS)
 - BPH Impact Index (BPHII)
 - International Index of Erectile Function (IIEF)
 - Male Sexual Health Questionnaire Short Form (MSHQ-EjD Short Form)
 - Prostate volume (PV), length and width, as measured by TRUS
 - Confirmation of function of detrusor muscles via urodynamics
- **Subjects must undergo a “washout” period of 6 months if they have been on:**
 - 5-alpha reductase inhibitor
 - Subject must undergo a “washout” period of 2 weeks if they have been on:
 - alpha blockers
 - antidepressants
 - anticholinergics
 - androgens
 - gonadotropin-releasing hormonal analogs
 - Subject must undergo a “washout” period of 1 week if they have been on:
 - Beta-blockers
 - Antihistamines
 - Anticonvulsants
 - Antispasmodics
 - Unless subjects have been on a stable dosing for the last 6 months (i.e. no changes)

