6.3 CONCOMITANT THERAPY

Therapy (medication and non-medication therapies) not restricted by a protocol requirement may be used during the study for the treatment or prevention of disease or to maintain good health. However, subjects should not take concomitant medications that affect the BPH symptoms which might confound the study result, per the PI's discretion.

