6.4 SUMMARY OF PRE-PROCEDURE PREPARATION

CONFIDENTIAL: Contains Proprietary Information

All eligible subjects who have signed an informed consent and are on alpha blockers or beta blockers will undergo a washout period of 2 weeks or 7 days, respectively. Subjects who have been on a stable dosing of beta blockers for the last 6 months (i.e. no dose changes) do not need to undergo the 7 day washout period.

Subjects are to be given an oral anti-anxiety medication prior to treatment. This medication must be given at least 45 minutes prior to the procedure, but no more than 2 hours before the procedure. No anesthesia will be allowed. Pain killer may be prescribed at the physician's discretion.

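### Phase 2 drug washout ends before enrolment, so persisting washout events are excluded as AEs, washout failures go uncounted, and 6.1 conflicts with 6.2 and 6.4 on when consent is signed

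*Combined protocol and SAP*

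**What the plan says.** **Washout.** Protocol 5.5 items 13 and 14, with 6.2, require Phase 2 candidates to be off ten drug classes for set periods before treatment. The four 1-week classes carry an exemption, "unless there is documented evidence of stable dosing for last 6 months"; the 2-week and 6-month classes do not.

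**Enrolment and consent in 6.1.** The candidate is given the consent form to read. Then: "Subjects that were on BPH medication will then go through a washout period". Next: "If the subject successfully goes through the washout period and still meets the selection criteria, the subject will be considered enrolled", with an enrolment ID. The following paragraph has the investigator or coordinator review the form with him: "Upon completion, the subject will be given an opportunity to sign the informed consent". It closes with a second definition: "A subject will be considered officially enrolled only if treatment with the NxThera Rezūm System is attempted".

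**Consent elsewhere.** Section 6.2 lists the washouts under this introduction: "The following evaluations will be completed for all study candidates who have provided a written informed consent". Section 6.4 says: "All eligible subjects who have signed an informed consent and are on alpha blockers or beta blockers will undergo a washout period". Section 11.2 requires a dated signature before enrolment and does not mention washout.

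**Adverse events.** Section 7.1 starts the AE period once the study procedure has begun, without defining that term. It leaves out conditions already present at enrolment unless they become worse to a clinically significant degree. Table 6-2 has no AE tick at baseline.

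**Accounting.** Section 14.2 undertakes to account for enrolled subjects, including those withdrawn or lost. No section asks for a screening log or a report of screen failures.

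**The concern.** Washout is something the protocol does to these men for study purposes. Section 6.3 recognises that drugs can alter the outcome, since "subjects should not take concomitant medications that affect the BPH symptoms". Stopping them can therefore bring symptoms back, and the list also includes antidepressants and androgens, with no stable-dose exemption. Harm arising in that interval is harm from a study step, yet the AE definition and the accounting are both tied to enrolment, which comes later.

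Two kinds of men could drop out of view. One deteriorates until he fails the post-washout eligibility check, for example with a PVR of 300 ml or more against the limit in 5.4 item 4. The other develops a problem that breaks no criterion, and is enrolled with it classed as pre-existing. The safety report would then not show what washout cost, or how many men were lost in reaching up to 15 treated. Separately, a site that followed 6.1 in the order written would stop a drug for research before holding a signature.

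**Working it through.** There is no figure in the plan to reproduce. The check sets the sections side by side.

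**1. Timing.** Enrolment is either passing the post-washout eligibility check or attempted treatment (both in 6.1). Both come after washout. Section 10.1 assigns the enrolment number as each man is enrolled, so a man in washout has no study ID yet.

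**2. AE capture.** The term study procedure has two tenable readings. It may include washout: Section 6, which contains the washout, is titled Study Procedures. Or it may mean the index procedure, the only anchor that 7.7 uses for causality.

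| Event | Reading includes washout | Reading is index procedure |
|---|---|---|
| Starts in washout, persists to enrolment, no clinically significant worsening | Excluded: present at enrolment | Excluded |
| Starts and resolves in washout | Can be recorded (7.1, 7.6) | Not an AE |
| Baseline LUTS worsens in washout to a clinically significant degree | Can be recorded: increased severity | Not an AE |
| Occurs in a man never enrolled | Can be recorded under 7.6 | Not an AE |
| Starts in washout, then worsens significantly after treatment | AE | AE |

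Only the first row is lost on both readings. The next three turn on the undefined term.

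**3. Accounting under 14.2.**

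- Fails washout: not enrolled under either definition, so outside the accounting.
- Passes washout, never treated: enrolled under the first definition, so counted; not enrolled under the second, so not counted.
- Treatment attempted: counted under both.

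**4. Consent.** The narrative order in 6.1 is read, wash out, be enrolled, review, sign. Sections 6.2 and 6.4 put the signature first, though 6.4 names only alpha and beta blockers. Section 11.2 would be met by a signature after washout but before enrolment. So 6.1 conflicts with 6.2 and 6.4, and 11.2 does not settle the conflict.

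**5. Counts.**

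- Drug classes in 5.5 item 13: 4 (1 week, stable users exempt) + 5 (2 weeks) + 1 (6 months) = 10, of which 5 + 1 = 6 have no exemption.
- Table 6-2 has 9 columns. AEs are ticked in 8, with baseline the only blank; medications are ticked in all 9.
- Scheduled AE checks in the 6 months after treatment: day 1, week 1, months 1, 3 and 6 = 5. In a 6-month washout: 0.

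**6. Illustration only.** The documents give no washout-failure rate. If a share f of all candidates failed washout, treating 15 men would need 15/(1 − f) starters, rounded up:

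- f = 5%: 15/0.95 = 15.8, so 16 starters and 1 uncounted
- f = 10%: 15/0.90 = 16.7, so 17 and 2
- f = 20%: 15/0.80 = 18.75, so 19 and 4
- f = 30%: 15/0.70 = 21.4, so 22 and 7

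**The case against.** The best defence is that collecting device AEs from the procedure onward is a legitimate scope choice in a descriptive study of up to 15 men whose safety objective concerns the device. That stands for device AE rates. It does not answer the accounting gap or the consent conflict.

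A reader might infer three stronger claims, none of which the documents support.

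- *That the plan stops drugs without consent.* Sections 6.2 and 6.4 put signed consent first. Section 11.5 treats failure to obtain consent as a deviation, and Table 13-1 has it reported within 5 working days. In 6.1 the words about completion follow the consent review and need not refer to washout, so the order there is narrative and not a timing rule. What stands is an internal conflict.
- *That all washout events are lost.* Section 7.1 counts increased severity of a pre-existing condition, so worsening LUTS in washout could be an AE if the study procedure includes washout.
- *That every untreated man disappears.* A man who passes washout is enrolled under the first definition.

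Other provisions narrow the gap, because the protocol sometimes calls men before treatment subjects. Section 14.5.1 asks for a documented reason for withdrawal and for AE follow-up, 14.3 provides for AE forms at unscheduled visits, 13.2 covers case histories, and Table 13-1 covers deaths and withdrawals. None of them requires washout failures or washout events to be tabulated.

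A fair caution also concerns the remedy. Some return of LUTS off drug is foreseeable, and the 72-hour allowance in 7.1 applies only after the procedure. Recording from consent without a rule for expected symptom return would generate uninformative AEs.

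**Conclusion.** The point holds within limits. On any reading, a non-fatal event that starts in washout and persists without clinically significant worsening is excluded as an AE, and men who fail washout are outside the 14.2 accounting. Capture of other washout events, including worsening LUTS, depends on an undefined term. Men who pass washout but are not treated are uncounted only under the attempted-treatment definition. The consent issue is a conflict in wording between 6.1 and Sections 6.2 and 6.4, which 11.2 leaves open.

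The exposed interval is 1 week, 2 weeks or 6 months, with no scheduled AE check. How many men or events are involved cannot be stated, because the documents give neither the number on these drugs nor any event rate. The conclusion rests on what the plan requires; a site may keep a log voluntarily. It would be wrong to infer that the device results are biased: Phase 2 endpoints and device AE rates are unaffected. The case for a change is protection of the men in washout and complete safety reporting, and it merits a short amendment.

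**What to change.** - **6.1:** require signed consent before any drug is stopped, consistent with 6.2 and 6.4, and keep one definition of enrolment.
- **7.1 and 7.7:** record SAEs and clinically significant AEs from signed consent for every man who starts washout, and judge pre-existing conditions as of consent. Check at the post-washout reassessment that 6.1 already requires, or when he leaves washout if that is sooner, and show this as a baseline tick in Table 6-2. Treat return of LUTS to the expected off-drug level as an expected washout effect unless it needs intervention. Add a category in 7.7 for events related to washout.
- **14.2:** report how many men start washout, with the reason for each who is not treated, and list washout events apart from device AEs so that device rates do not change.

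The cost is a short amendment, a screening and washout log, and some extra AE recording, including a contact with men who leave washout early. No additional treated subjects or tests are needed.

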6.2 SCREENING AND BASELINE EVALUATIONS

The following evaluations will be completed for all study candidates who have provided a written informed consent:

- Complete general medical and genitourinary history (including any previous treatment for LUTS; if pharmacologic, name of drug(s) as well as dosage) and duration of subject's BPH symptoms.**
- Blood analysis:**
 - Complete blood cell count (CBC)**
 - Blood urea nitrogen (BUN)**

- Serum creatinine
- Serum prostate-specific antigen (PSA) level
- Electrolytes
- **Uroflowmetry:**
 - Voided volume (must be ≥ 125 mL or test must be repeated)
 - Total time of voiding
 - Peak flow rate (Q_{max}; also known as PFR)
 - Average urinary flow rate
 - Post-void residual urine volume (PVR; may be measured by either ultrasound or catheterization but the same method must be used pre- and post-treatment)
- **Urinalysis**
 - Urine culture, if indicated
 - Subject questionnaires:
 - International Prostate Symptom Score (IPSS)
 - BPH Impact Index (BPHII)
 - International Index of Erectile Function (IIEF)
 - Male Sexual Health Questionnaire Short Form (MSHQ-EjD Short Form)
 - Prostate volume (PV), length and width, as measured by TRUS
 - Confirmation of function of detrusor muscles via urodynamics
- **Subjects must undergo a “washout” period of 6 months if they have been on:**
 - 5-alpha reductase inhibitor
 - Subject must undergo a “washout” period of 2 weeks if they have been on:
 - alpha blockers
 - antidepressants
 - anticholinergics
 - androgens
 - gonadotropin-releasing hormonal analogs
 - Subject must undergo a “washout” period of 1 week if they have been on:
 - Beta-blockers
 - Antihistamines
 - Anticonvulsants
 - Antispasmodics
 - Unless subjects have been on a stable dosing for the last 6 months (i.e. no changes)

6.3 CONCOMITANT THERAPY

Therapy (medication and non-medication therapies) not restricted by a protocol requirement may be used during the study for the treatment or prevention of disease or to maintain good health. However, subjects should not take concomitant medications that affect the BPH symptoms which might confound the study result, per the PI's discretion.

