Purpose:	To evaluate the effect of the NxThera BPH Rezūm System on prostate tissue in subjects suffering from LUTS symptoms secondary to benign prostatic hyperplasia (BPH).
Study Design:	
This study is a single center study. It will be carried out in two phases on subjects with benign prostatic hyperplasia.
 
Phase 1: Acute study - In-vivo treatment of the prostate in subjects scheduled to have a surgical TURP or full excision of the prostate. Prostate tissue will be excised after treatment as part of the planned surgery. There is no follow up.
 
Phase 2: Optimization study - Subjects with BPH symptoms will be treated with the Rezūm device with a range of thermal energies (as measured by calorie output) to optimize the setting for maximum lesion size with minimal intra and post procedure discomfort. The lesion size and ablated tissue resorption rate will be followed post-procedure via MRIs.

Enrollment:	
Phase 1: Up to 20 BPH subjects scheduled for surgical removal of the BPH tissue
 
Phase 2: Up to 15 BPH subjects suffering from BPH symptoms.

Target Subject Population:	
 • Male subjects \geq 45 years of age who have symptomatic / obstructive symptoms secondary to BPH requiring surgical intervention.
Follow-up:	
Phase 1 – Acute, no follow up
 
Phase 2 – 1 day, 1 week, 1 month, 3 months, 6 months, 12 months, and annually thereafter up to 5 years.

Phase 1 Endpoint	Lesion size and characteristics as evaluated using Tetrazolium Chloride (TTC) stain and histopathologic evaluation of representative samples.
Phase 2 Endpoints	
Lesion characterization via MRI
 
Intra and post procedure discomfort
 
Catheterization post procedure
 
The change (improvement) from baseline in International Prostate Symptom Scores (IPSS) at day 1, week 1, month 1, months 3,6 and 12, and annually thereafter up to 5 years

CONFIDENTIAL: Contains Proprietary Information

Study and Data Management:	Libra Medical, Inc. [name] [contact] [contact] Email: [contact]
Study Monitors:	Libra Medical, Inc. [name] [contact] [contact] Email: [contact]
Sponsor:	NxThera Inc [name] [contact]

TABLE OF CONTENTS

1	BACKGROUND.....	8
2	SUMMARY DEVICE DESCRIPTION.....	8
3	SUMMARY OF PROCEDURE	9
4	PHASE I ACUTE STUDY DESIGN.....	12
5	PHASE 2: OPTIMIZATION STUDY	13
6	STUDY PROCEDURES	15

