AEs should be classified according to their underlying cause, if known, (e.g., fever resulting from infection should be reported as “infection”). Concomitant AEs that are unrelated (in the clinician’s judgment) should be reported as separate events.

AE determination is based on three levels of evidence:

Level 1 – final diagnosis

Level 2 – signs

Level 3 – symptoms

Every effort should be made to collect Level 1 evidence of any AE. If an AE has all three levels of evidence, an AE should be reported only once at the highest level of severity, which is the final diagnosis (Level 1). A single AE should not be reported as multiple AEs based on separate symptoms, signs, and diagnosis.

In cases where a diagnosis is not possible, AE determination should be based on the next highest level of evidence (signs, Level 2), followed by symptoms (Level 3), if only symptoms are available.

A corrective action itself is not an AE. The AE should always be determined based on the reason that a corrective action was taken.

Note: there may be multiple symptoms representing or associated with only one AE. In this case only one AE should be reported. The symptoms can be captured within the AE description. If the symptoms are related to LUTS, complete the LUTS form in addition to the AE form. If AE requires catheterization, then complete the catheterization form.

Figure 7-1 is an AE determination and outcome flowchart.

[figure not shown]

Figure 7-1: AE Determination and Outcome Flowchart

Examples

Subject is diagnosed with urinary retention and requires catheterization for more than 3 days. In addition, they have symptoms of irritation, urgency, and hematuria. Only one AE – retention should be reported. The additional symptoms should be noted in the AE description. Catheterization is the treatment.

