14.2 STATISTICAL ANALYSIS

Descriptive statistics will be calculated and reported for study variables, as appropriate. Continuous variables (e.g., symptom score, uroflowmetry, quality of life assessments) will be summarized using statistics such as means, standard deviations and absolute change from baseline. Categorical variables (e.g., adverse events) will be summarized as frequency

distributions. Adverse events and technical observations will be reported by frequency of occurrence, severity and relationship to the vapor treatment device.

All subjects enrolled in this study (including those withdrawn from the study or lost to follow-up) will be accounted for and documented.

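### The plan sets no rule for IPSS scores after BPH retreatment, so by default they enter the mean change to year 5 and read as device benefit

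*Combined protocol and SAP*

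**What the plan says.** The synopsis lists as a Phase 2 endpoint "The change (improvement) from baseline in International Prostate Symptom Scores (IPSS) at day 1, week 1, month 1", continuing through months 3, 6 and 12 and then "annually thereafter up to 5 years". Section 5.3.4 gives the same endpoint as "Change in IPSS score from baseline at various points post-procedure". Table 6-2 schedules IPSS at every visit through year 5.

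The analysis text is section 14.2: continuous variables "will be summarized using statistics such as means, standard deviations and absolute change from baseline". Section 14.8 adds that baseline questionnaires are compared with those from each follow-up visit in order to judge the effect of treatment. Neither section separates men who have been retreated.

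On other treatment, section 6.3 allows any drug or non-drug therapy that the protocol does not restrict. It then says that "subjects should not take concomitant medications that affect the BPH symptoms which might confound the study result", subject to the investigator's judgement. No section restricts a repeat BPH procedure during follow-up. Under 14.6 a subject exits at study end or after the 5-year visit, so retreatment is not an exit event. Section 14.5.3 lets the investigator withdraw a subject at discretion.

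On capture, section 7.1 states "A corrective action itself is not an AE" and then directs that the AE be identified from the reason for the action. The AE form records treatments given (7.6), and medications are logged at every visit to year 5 (Table 6-2). Re-intervention is not an endpoint and has no row in Table 6-1 or Table 6-2.

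**The concern.** The protocol takes care that the baseline is clean. Section 5.5 excludes men with a prior BPH procedure, sections 5.5 and 6.2 require washout of alpha blockers and 5-alpha reductase inhibitors, and section 6.3 recognises that symptom-modifying drugs can confound the result. After treatment, no matching rule protects the follow-up scores. A score taken after later surgery, or on a restarted drug, minus an unoperated and drug-free baseline does not measure the device alone.

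Retreatment is foreseeable. Section 14.1 describes the Phase 2 population as men who would otherwise have had surgery or another minimally invasive treatment. If the device wears off in some of them and other treatment then restores their scores, the late IPSS mean can look stable while part of it is owed to that other treatment. There is no control arm to reveal this, and the descriptive means are the whole IPSS result.

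**Working it through.** **Figures in the plan.** None can be reproduced. The documents give no expected IPSS change, SD, retreatment rate or dropout rate. The usable inputs are the Phase 2 cap of 15 subjects (section 5.2) and the entry requirement of a baseline IPSS of at least 15 (section 5.4). Everything else below is an assumption.

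**Formulas.** Let k be the number retreated among 15 men seen at a visit, R the mean IPSS change in the others, and *pre* and *post* the mean changes in the retreated men before and after retreatment.

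- Scores kept: [(15 − k)R + k·post]/15
- Pre-retreatment value carried (failure): [(15 − k)R + k·pre]/15
- Retreated men dropped: R
- Kept minus carried: (k/15)(post − pre)
- Kept minus dropped: (k/15)(post − R)

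Each retreated man carries 1/15 = 6.7% of the mean. If fewer than 15 are seen at a late visit, that number replaces 15 and each man weighs more.

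**Results under assumed inputs** (negative is improvement):

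| Assumed R, pre, post | k | Kept | Carried | Dropped | Overstatement, kept against carried |
|---|---|---|---|---|---|
| −10, 0, −10 | 1 | −10.00 | −9.33 | −10 | 0.67 |
| | 3 | −10.00 | −8.00 | −10 | 2.00 |
| | 5 | −10.00 | −6.67 | −10 | 3.33 |
| −10, −3, −12 | 1 | −10.13 | −9.53 | −10 | 0.60 |
| | 3 | −10.40 | −8.60 | −10 | 1.80 |
| | 5 | −10.67 | −7.67 | −10 | 3.00 |
| −15, 0, −15 | 1 | −15.00 | −14.00 | −15 | 1.00 |
| | 3 | −15.00 | −12.00 | −15 | 3.00 |
| | 5 | −15.00 | −10.00 | −15 | 5.00 |
| −12, −2, −6 | 1 | −11.60 | −11.33 | −12 | 0.27 |
| | 3 | −10.80 | −10.00 | −12 | 0.80 |
| | 5 | −10.00 | −8.67 | −12 | 1.33 |

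Worked line, last scenario with k = 3: kept = (12 × −12 + 3 × −6)/15 = −162/15 = −10.8; carried = (12 × −12 + 3 × −2)/15 = −150/15 = −10.0.

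In the first scenario the kept mean is −10.0 whatever k is, so the mean alone cannot show how many men needed further treatment. In the last scenario, where retreatment works less well than the device, dropping the men (−12.0) flatters the device more than keeping them (−10.8).

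**Chance that the issue arises.** The probability of at least one retreated man among 15 is 1 − (1 − p)^15. For assumed 5-year rates p of 5%, 10%, 20% and 30% it is 0.537, 0.794, 0.965 and 0.995.

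**The case against.** **The documents are silent; they do not say that the scores stay in.** A reader might infer that the plan prescribes averaging them in. It does not. The list of statistics in 14.2 is open-ended, and withdrawal under 14.5.3 could remove the values instead. This stands. Inclusion is the default reading of 14.2 and 14.8, not a stated rule. The alternative does not cure the problem, because dropping these men can flatter the device as much or more.

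**Failures would not be invisible.** A reader might infer from "A corrective action itself is not an AE" that retreatments disappear. The same paragraph of 7.1 requires the reason for the action to be recorded as the AE. Urinary symptoms that arise outside the 72-hour window, or recur after resolving, count as AEs, the AE form records treatments given, and drugs are logged to year 5. A man operated on for recurrent symptoms would normally appear somewhere. What remains is narrower: a man who merely returns to his baseline state may not meet the change-from-baseline AE definition, and no one is asked to count retreatments.

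**The bias need not grow with every failure.** A reader might infer that more failures always prop up the late mean. Where retreatment works less well than the device, keeping the scores gives a worse mean than dropping the men. The overstatement is measured against the failure-carried value and exists only if retreatment lowers IPSS.

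**The stakes are modest.** Phase 2 varies power and water flow, and section 5.2 names the acute response as its unknown. IPSS is the fourth of four endpoints, with no hypothesis test and no stated durability objective. This also stands. It limits the importance of the point without closing the gap, since IPSS change is still to be reported to year 5.

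**Failure carried forward is itself a choice.** Triggered by any new drug, it could freeze a man at an early post-procedure score for five years because of one short course. This is a fair criticism, so it should neither be the sole headline nor be triggered by brief courses.

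**Conclusion.** The point holds in this form: the plan has no rule for IPSS after a BPH re-intervention or during ongoing new BPH medication. By default those scores enter the mean change to year 5 and are read as a device effect, although section 6.3 recognises such medication as confounding. Retreatment is only partly captured and is never tabulated.

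The size cannot be known from the documents. Against the failure-carried summary, it is (k/15) times the IPSS gain due to retreatment. Across the assumed scenarios that is 0.27 to 1.0 points at k = 1, 0.8 to 3.0 at k = 3 and 1.33 to 5.0 at k = 5. This rests on 15 men being seen, on the assumed changes, and on retreatment lowering IPSS. It is worth settling before analysis, but it does not undermine a small descriptive study.

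**What to change.** In section 14.2, state that IPSS change at each visit will be shown two ways, side by side:

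- (a) all observed values;
- (b) values after a BPH procedure, or during sustained new BPH medication, treated as failure, for example by using the last pre-retreatment value. Short peri-procedural drug courses should not trigger this, and what counts as sustained should be defined for analysis before the data are examined.

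Report the number, type and timing of retreated subjects, and flag them in a per-subject listing, which is practical with at most 15 men. Add a dated BPH-retreatment field to the follow-up CRF; medications are already collected. Apply the same two summaries to Qmax only through month 12, because uroflow is not scheduled after that visit.

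This concerns data capture and analysis only and changes no treatment rule. The cost is one CRF field, one extra table and a listing. The downside is that the long-term improvement may look slightly smaller under (b).
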